3.3. Expected Duration of Treatment and Subject Participation

Each course of radiation therapy will be 3-5 fractions delivered over 3-21 days. The first course of radiation will be initiated at any time point between the date of cycle 1 of immune therapy through the date of cycle 2 of immune therapy. The duration of immune therapy administration and the number of courses of radiation therapy that a subject receives will be dependent upon the subject's response to prior treatment. There is no specific maximum number of cycles of immune therapy if a patient continues to respond to treatment, or courses of radiation therapy if a patient has persistent stable disease on imaging. Progressive disease will be defined per irRC criteria as assessed by two imaging studies \geq 4 weeks apart. Because abscopal responses have been reported even when the radiation is given after the immune therapy was completed, a final course of radiation therapy will be offered to patients at the time of progressive disease on imaging.³⁸⁻³⁹ Subsequent therapy decisions will be at the discretion of the treating physicians, including the option of continuing the immune therapy past progression if clinically indicated.

The radiation therapy or immune therapy may be cancelled or discontinued at any point if no longer medically advisable due to intercurrent illness, toxicity/adverse event, decline in performance status, pregnancy, the best interests of the patient, or death. Subjects may also withdraw consent from treatment (partial consent) or from the study (full consent).

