3.4. Duration of Follow-Up

Follow-up of subjects should continue for 30 days after systemic disease progression or initiation of an alternate systemic therapy (whichever comes first). After the study period, the sponsor-investigator may still obtain data from a subject's medical records or by phone call in order to document overall survival per patient agreement. Any adverse events experienced after a patient has discontinued the study treatment will be followed until resolution, stabilization, or until it has been determined that the study treatment or participation is not the cause. Serious adverse events that are still ongoing at the end of the study period will necessitate follow-up to determine the final outcome. Any serious adverse event that occurs after the study period and is considered to be possibly related to the study treatment or study participation will be recorded and reported immediately.

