5.3. Subsequent Response-Adapted Radiation Therapy

Any patient who completes the initial course of radiation therapy and continues on one of the immune checkpoint inhibitors described above will be eligible for subsequent course(s) of radiation therapy to a different lesion that was not previously irradiated based on the results of follow-up imaging studies detailed below and in section 11.

- Patients with a partial or complete response per irRC criteria will be observed without any further radiation therapy until progression.
- Patients with stable disease per irRC criteria will undergo an additional course of radiation therapy given concurrently with the next cycle of immune checkpoint

- therapy, and then continue the immune therapy as above. Each subsequent course of radiation therapy should ideally be at least 2 months after completion of the prior course of radiation therapy, but is left at the discretion of the treating physician depending on the patient's palliative needs. Day 1 of radiation should be on Day 1 of the next cycle of immune therapy.
- Patients with progressive disease at any time per irRC criteria will undergo a final course of radiation therapy. This may be given concurrently with a final cycle of immune therapy or as stand-alone treatment within 6 weeks after discontinuation of immune therapy but before an alternative systemic therapy is initiated.

Please see Section 5.5 below regarding situations in which these subsequent courses of radiation therapy may be withheld. Each subsequent course of radiation therapy should be given in a similar style as detailed for the initial course of radiation therapy above. In patients with a mixed response to therapy, preference will be given to an enlarging tumor (rather than one that is stable or decreasing in size) as the site of treatment. Reimaging will again be obtained after completion of the radiation therapy with timing at the discretion of the treating physicians, and the same response-adapted approach to decision making for further courses of radiation therapy will be carried out as described above.

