11.2. Response Criteria

The irRC criteria for assessing systemic disease response (including only non-irradiated lesions) can be seen in the following table:

New, measurable lesions (ie, $\geq 5 \times 5$ mm)	Incorporated into tumor burden
New, non-measurable lesions (ie, $< 5 \times 5$ mm)	Do not define progression (but preclude irCR)
Non-index lesions	Contribute to defining irCR (complete disappearance required)
irCR	Disappearance of all lesions in two consecutive observations at least 4 weeks apart
irPR	$\geq 50\%$ decrease in tumor burden compared with baseline in two observations at least 4 weeks apart
irSD	Neither sufficient decrease in tumor burden to qualify as irPR

	nor sufficient increase in tumor burden to qualify as irPD.
irPD	$\geq 25\%$ increase in tumor burden compared with nadir (at any single time point) in two consecutive observations at least 4 weeks apart.

Examples of irRC overall response³⁷:

Measurable response Index and new, measurable lesions (tumor burden),* %	Nonmeasurable response		Overall response Using irRC
	Non-index lesions	New, nonmeasurable lesions	
↓100	Absent	Absent	irCR [†]
↓100	Stable	Any	irPR [†]
↓100	Unequivocal progression	Any	irPR [†]
↓≥50	Absent/Stable	Any	irPR [†]
↓≥50	Unequivocal progression	Any	irPR [†]
↓<50 to <25↓	Absent/Stable	Any	irSD
↓<50 to <25↓	Unequivocal progression	Any	irSD
≥25↓	Any	Any	irPD [†]

*Decreases assessed relative to baseline, including measurable lesions only (>5 x 5 mm).
†Assuming response (irCR) and progression (irPD) are confirmed by a second, consecutive assessment at least 4 wk apart.

RECIST version 1.1 will be used to assess the local response of irradiated lesions only, taking as reference the baseline largest diameter:

Complete Response (CR)	Disappearance of the irradiated lesion
Partial Response (PR)	$\geq 30\%$ decrease in the single largest diameter of the irradiated lesion
Stable Disease (SD)	Neither sufficient decrease in diameter to qualify as PR nor sufficient increase in diameter to qualify as PD
Progressive Disease (PD)	$\geq 20\%$ increase in the single largest diameter of the irradiated lesion. In addition to the relative increase of 20%, the sum must also demonstrate an absolute increase of at least 5 mm (0.5 cm).

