11.2.2. Progression-Free Survival

The duration of time from start of treatment to time of progression or death, whichever occurs first. For those patients with a CR or PR, the reference for progressive disease the smallest measurements recorded since the treatment started).

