13.2. Sample Size/Accrual Rate

The primary analysis will be for patients enrolled at time-points (A) and (B) above, whereas patients enrolled at time-point (C) will be included in observational analysis only (see section 3.1). The primary endpoint of this study is the overall response rate (complete + partial response) and the efficacy will be assessed using the Simon's two-stage Minmax design. A sample size of 33 patients is chosen to differentiate between the response rate of 20% and 40% with 80% power at a significance level of 0.05. In particular, 18 patients will be enrolled at the first stage. If 15 or more of the first 18 patients have disease progression prior to any response, the trial will be terminated; otherwise an additional 15 patients will be treated for a total of 33 patients. In the final data analysis, if 10 or fewer patients respond among 33 patients, the treatment will be concluded ineffective. The probability of early termination due to futility is 0.72.

For correlative study between biomarkers and response, this sample size will have at least 80% power to detect a 50% change/difference on biomarker data between response and non-response groups using a two-sided two-sample t-test at 0.05 significance level, assuming that the response rate is 35% or higher and the coefficient of variation (CV) of biomarkers is 0.45.

Approximately 100 patients with metastatic NSCLC are diagnosed and treated each year at our institution, many of whom will be candidates for immune checkpoint therapy. As such, we expect to accrue 3 patients per month to this trial for an estimated accrual period of one year. The full estimated duration of the study is two years.

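### The stage-1 futility rule and the stated early-termination probability in section 13.2 do not agree: 15 of 18 gives at most 0.50, not 0.72

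*Combined protocol and SAP*

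**What the plan says.** Section 13.2 names a Simon two-stage minimax design for the overall response rate, 20% against 40%, with 80% power at a significance level of 0.05. Eighteen patients enter stage 1. The interim rule is: "If 15 or more of the first 18 patients have disease progression prior to any response, the trial will be terminated". Otherwise 15 more are treated, for 33 in total, and 10 or fewer responders of 33 means the treatment is judged ineffective. The paragraph ends: "The probability of early termination due to futility is 0.72".

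Progression is defined elsewhere. Section 3.3 says: "Progressive disease will be defined per irRC criteria as assessed by two imaging studies", at least 4 weeks apart. The irPD row in section 11.2 requires a 25% or greater "increase in tumor burden compared with nadir (at any single time point) in two consecutive observations at least 4 weeks apart". Death joins progression only in the definition of progression-free survival in section 11.2.2: "The duration of time from start of treatment to time of progression or death, whichever occurs first". No other section restates the interim rule or reconciles it with 0.72.

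**The concern.** A two-stage design fixes a stage-1 cut-off, and the early-termination probability at the null rate follows from it exactly. Here the cut-off and the probability stand in the same paragraph and can be checked against each other. If they disagree, one of them is wrong. A monitor who sees 14 progressions and 4 responses would continue under the written rule, whereas the design that yields 0.72 would stop.

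The rule also counts progressions although the endpoint is response. A non-responder who dies before progression is documented, or who moves to another systemic therapy first, does not literally count toward stopping. At stake is how often a combination no better than 20% goes on to a second stage of 15 patients.

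**Working it through.** **Inputs, all from section 13.2:** null rate 0.20, alternative 0.40, stage 1 of 18, total 33, ineffective at 10 or fewer responses, stated early termination 0.72.

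**1. Reproduce the 0.72.** Let X be the number of responders among 18 at a rate of 0.20. The exact binomial probabilities are:

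| X | P(X) | Cumulative |
|---|---|---|
| 0 | 0.0180 | 0.0180 |
| 1 | 0.0811 | 0.0991 |
| 2 | 0.1723 | 0.2713 |
| 3 | 0.2297 | 0.5010 |
| 4 | 0.2153 | 0.7164 |

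The stated 0.72 is P(X ≤ 4), that is, 14 or more of 18 without a response.

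**2. The rule as written.** Fifteen or more progressing before response implies X ≤ 3. Even if every non-responder has progressed, the probability is P(X ≤ 3) = 0.501. Patients who progress before responding cannot outnumber non-responders, so 0.501 is a ceiling.

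**3. Which design do the other figures belong to?** I searched all two-stage designs for 0.20 versus 0.40 with type I error at most 0.05 and power at least 0.80, working upward in total size. The smallest feasible total is 33. Among 33-patient designs, the lowest expected sample size at the null belongs to 4/18 then 10/33. The next two are 3/16 (early termination 0.598) and 2/13 (0.502), which have other stage-1 sizes. The stated 18, 33, 10 and 0.72 all fit a cut-off of 4.

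**4. Operating characteristics.** With r1 the stage-1 cut-off, P(declare effective) = Σ over x > r1 of P(X₁ = x) · P(X₂ ≥ 11 − x), where X₁ is binomial on 18 and X₂ binomial on 15. Expected N = 18 + 15 × (1 − early termination).

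| | r1 = 3 (as written, best case) | r1 = 4 |
|---|---|---|
| Early termination at 20% | 0.501 | 0.716 |
| Expected N at 20% | 18 + 15 × 0.499 = 25.5 | 18 + 15 × 0.284 = 22.3 |
| Type I error | 0.0497 | 0.0458 |
| Power at 40% | 0.825 | 0.801 |
| Early termination at 40% | 0.033 | 0.094 |

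The difference in expected N is 25.5 − 22.3 = 3.2 patients.

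**5. Bound for the progression wording.** Uncounted non-responders can only lower the stopping probability. In the extreme where the trial never stops, a single stage of 33 with 11 or more responses has type I error 0.0508 and power 0.831. The final test therefore barely moves, whatever the number uncounted.

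**The case against.** The best defence is that waiting for progression is deliberate. Section 11.1.2 notes that immune responses can be slow, and under section 5.3, "Patients with stable disease per irRC criteria will undergo an additional course of radiation therapy", so a stable patient may still respond. This stands as a reason for the wording. It does not explain how 15 and 0.72 can both be right.

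The written rule, read as 3/18 then 10/33, also meets both stated error targets. That stands too. What fails is the stated early-termination probability.

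A reader might go further in three ways that the documents do not support.

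- *Stable patients never count, so the rule hardly works.* The plan follows patients to progression: section 3.5 ties the primary analysis to the last subject's progression, and section 11.1.1 keeps imaging at intervals of 4 months or less. A stable patient is not yet counted, rather than lost. Switching is limited as well. Section 5.2 continues the checkpoint inhibitor until progression or unacceptable toxicity, and section 3.4 says: "Follow-up of subjects should continue for 30 days after systemic disease progression or initiation of an alternate systemic therapy". Section 11.1.1 only recommends the confirmatory scan. Some patients who switch may therefore still be counted. No rate of death or switching is given, so the further loss cannot be calculated.
- *An inactive regimen is carried forward.* The 20% null lies within the 19–25% that section 2.2 reports for checkpoint inhibitors. At the null, patients still receive standard immune therapy; what is extra is the radiation.
- *The 15 is certainly the slip.* The minimax match makes that likely, but the documents cannot exclude that 15 was meant and 0.72 is the wrong figure.

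**Conclusion.** The point holds as an internal inconsistency in section 13.2. At a 20% response rate the written rule stops the trial with probability at most 0.50, against the stated 0.72. A combination that adds nothing passes stage 1 with probability at least 0.499 rather than 0.28, at a cost of about 3 more expected patients. The 0.50 is exact and assumes only that each non-responder among the 18 has progressed when the rule is read. Deaths and therapy switches before documented progression can only lower it, by an amount the documents do not allow to be calculated.

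It would be wrong to infer that the trial's final conclusion is compromised. Type I error is 0.0497 in the best case and about 0.051 if the trial never stops early, and power is at least 0.80 throughout. The defect lies in the futility protection and in what readers of 13.2 are told about it.

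**What to change.** Amend section 13.2 in one of two ways.

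- **(a)** Stop if 4 or fewer of the first 18 patients have a confirmed irCR or irPR. This restores 0.72 (type I error 0.046, power 0.801, expected N 22.3). The cost is a higher risk of stopping at a true 40%, from at most 3.3% to 9.4%, and almost no slack in power. If 5%, 10% or 20% of responders were confirmed only after the look (an assumption; the documents give no figure), power would be 0.78, 0.75 or 0.67.
- **(b)** Stop if 3 or fewer of the first 18 have a confirmed irCR or irPR, and correct 0.72 to 0.50 (type I error 0.0497, power 0.825, expected N 25.5). This tolerates late responses better: power is 0.82, 0.81 or 0.77 under the same assumption. The cost is weaker futility protection, now stated correctly.

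Either is defensible; the choice depends on how late the sponsor expects responses to appear. In both, word the rule in responses, and count death or the start of another systemic therapy before response as non-response. Such patients stay among the 18 even if section 11.1.2 would call them non-evaluable. Section 13.2 gives no time for the stage-1 look, so one should be stated; its length is the sponsor's choice. The change is a few sentences and needs no new data.

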9.1.3. Collection of Specimens

After consenting patients, peripheral blood samples will be collected at baseline before initiation of treatment and at the time of any change in response status as assessed on follow-up imaging studies. All attempts will be made to draw the blood with currently scheduled venipuncture, but it will also be permissible to draw specifically for this study if necessary.

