9.2.1. Background

Immune cell infiltration into malignant tumors is thought to be an important component of a patient having a response to immune checkpoint inhibitors and radiation, however, mechanisms of T-cell and macrophage trafficking have not been well studied in patients receiving immune checkpoint inhibitors or radiation. Changes in cytokine and chemokine levels specific for T-cells and macrophages may correlate with levels of circulating immune cells and tumor response to therapy.

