13.3. Methods for Analysis

Data will be summarized with respect to baseline characteristics and safety measurements using descriptive statistics (quantitative data) and contingency tables (qualitative data). The safety analysis will consist of AE summaries (frequency tables based on CTCAE grades) and laboratory abnormalities summary. For the primary endpoint, the response rate and its 95% confidence interval will be estimated with a binomial distribution. Univariate and multivariate logistic regression model will be used to assess the association between response and several radiotherapy variables (biologic effective dose,

number of lesions treated, sequence of radiation and immune therapy), tumor variables (irradiated tumor site, size, growth rate, histology, PD-L1 status, local response, extent of prior chemotherapy use, and biologic correlates), and patient variables (age, smoking status, and other factors associated with secondary immunodeficiency). A predictive nomogram for response will be developed based on the outcome of the multivariate analysis. In the data analysis on the secondary endpoints, the Kaplan-Meier method will be used to estimate overall survival and progression-free survival. Wilcoxon signed-rank test for paired data will be used to assess the change of quality of life scores between two visits. Since the lung cancer score (LCS) of the FACT-L focuses on lung cancer symptoms, this will be used for the primary QOL endpoint; however, the more general subscales of physical and functional well-being on the Trial Outcome Index (FACT-TOI) will also be collected. A difference of 3 LCS points will be considered clinically significant.¹²⁻¹³ Where applicable, comparison will be made to previous randomized trials assessing immune checkpoint inhibitors alone in a comparable patient population.

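### The biomarker analysis specifies no use of the patient's own baseline sample, and its 80% power holds for a single level but for a within-patient change only if the baseline/follow-up correlation is about 0.45 or higher

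*Combined protocol and SAP*

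**What the plan says.** Section 13.2 puts the power of the biomarker comparison at 80% or more and words it as follows: "to detect a 50% change/difference on biomarker data between response and non-response groups using a two-sided two-sample t-test at 0.05 significance level". Its inputs are a responder share of 35% or above and a biomarker coefficient of variation of 0.45. It names neither the sampling time nor whether the variable is a level or a change from baseline.

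Section 13.3 states: "Univariate and multivariate logistic regression model will be used to assess the association between response and several radiotherapy variables", followed by tumor and patient variables. Biologic correlates appear in that list without a sampling time or a baseline term. The only paired method in 13.3, the Wilcoxon signed-rank test, is for quality of life.

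The aims concern both baseline and change. Section 9.2.1 says: "Changes in cytokine and chemokine levels specific for T-cells and macrophages may correlate with levels of circulating immune cells and tumor response to therapy". Sections 9.1.2 and 9.2.2 want values from before and during therapy to help identify who benefits, and 9.3.2 is about how the immune repertoire evolves under treatment.

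The sampling schedule is given in two ways. The synopsis and section 1.3 plan a baseline sample, one at the first follow-up imaging, and more when response status changes. Section 9.1.3 says: "peripheral blood samples will be collected at baseline before initiation of treatment and at the time of any change in response status"; sections 9.2.3 and 9.3.3 say the same, and footnote 17 of the calendar (10.2) limits later draws to a change in extracranial response. The synopsis and section 2.5 restrict sampling to consenting patients.

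**The concern.** Responders and non-responders are not randomised groups, so they may already differ in a marker before treatment. If on-treatment levels are compared without the baseline, such a difference carries forward. The result cannot then separate a prognostic marker from an immune change under treatment, which is the distinction the correlative aims need. Baseline values that the trial already plans to collect would also go unused in a sample of 33.

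The word change/difference covers two quantities with different standard deviations (SDs), and only the SD of a level is given. The power claim cannot cover both without a stated correlation. Leaving the quantity open also allows a choice among level, change and adjusted results once the data are seen.

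**Working it through.** **Inputs from 13.2.** N = 33; 35% responders gives 11.55, so 12 v 21 or 11 v 22; difference 0.50 of the mean; SD 0.45 of the mean; two-sided 5%. **Assumed:** correlation rho between a patient's baseline and follow-up values, 0.3 to 0.7, because the documents give none. Every patient is taken to have both samples.

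**1. The plan's figure, for a level.** Standardised difference = 0.50/0.45 = 1.11. Noncentrality = 1.11/√(1/12 + 1/21) = 3.07, against a critical t of 2.04 on 31 degrees of freedom. Power is 84.5% (83.0% at 11 v 22). The stated 80% is reproduced.

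**2. The same test on change from baseline.** SD of change = 0.45 × √(2(1 − rho)). At 12 v 21:

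| rho | SD of change | Power |
|---|---|---|
| 0.3 | 0.532 | 71% |
| 0.4 | 0.493 | 77.5% |
| 0.5 | 0.450 | 84.5% |
| 0.7 | 0.349 | 97% |

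Power reaches 80% at rho = 0.44 (12 v 21) or 0.46 (11 v 22), hence about 0.45.

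**3. On-treatment level adjusted for baseline.** Residual SD = 0.45 × √(1 − rho²), which is 0.429, 0.390 and 0.321 at rho 0.3, 0.5 and 0.7. For a true 50% on-treatment difference with no baseline gap, simulated power is about 86%, 92% and 98%. The unadjusted level test has 84.5%, so the gain is about 2, 8 and 14 points.

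**4. Effect of a baseline gap.** Suppose responders differ by 50% at baseline. Two nulls are plausible: the gap regresses to rho × 0.50 at follow-up (0.25 at rho 0.5), or it persists at 0.50. Simulated rejection rates (12 v 21, SD 0.45) at rho 0.3 / 0.5 / 0.7:

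| Analysis | Gap regresses | Gap persists |
|---|---|---|
| On-treatment level, unadjusted | 15 / 32 / 54% | about 84% throughout |
| Change score | 42 / 32 / 21% | 5% throughout |
| Baseline-adjusted level | 5% throughout | 47 / 32 / 19% |

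The adjusted model gives fewer false signals than the unadjusted follow-up test under both nulls. It is not unbiased when the gap persists; there the change score is. When the gap regresses, the change score is the one that misleads.

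**5. Scale.** A coefficient of variation of 0.45 gives a log-scale SD of √ln(1 + 0.45²) = 0.43. For a 1.5-fold difference, ln(1.5)/0.43 = 0.94, and the unadjusted log-scale test has about 71% power at 12 v 21. With baseline adjustment this is about 75% at rho 0.3 and 94% at rho 0.7 (noncentral-t approximation). The stated 80% is therefore a raw-scale figure.

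**The case against.** Responders and non-responders are different patients, so a two-sample test is a valid form and a paired t-test would not answer the question. Section 13.2 never specifies an on-treatment comparison; the same test could be run on baseline levels or on change scores. For the aim of predicting benefit, a baseline difference is a result, not a bias. The analysis is correlative, carries no decision rule and does not touch the primary endpoint. All of this stands, and it makes the point one of specification.

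A reader might go further in four ways that the documents do not support:

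- That every patient gives a baseline and an on-treatment sample. Sections 9.1.3, 9.2.3 and 9.3.3 and footnote 17 of 10.2 tie the later sample to a change in response, so a patient whose status never changes may have baseline only. Sampling also needs consent.
- That the plan discards the baseline. It does not specify its use; change/difference may mean a change score.
- That the study is underpowered against its own claim. The 80% is reproduced for a level. The gain from adjustment is forgone power, and it rests on an assumed correlation.
- That baseline adjustment removes the problem and change scores are wrong. Each holds its 5% error rate under only one of the two nulls in step 4.

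**Conclusion.** The gap is real and moderate in weight. Sections 13.2 and 13.3 name an unadjusted two-sample test sized on a single level, and logistic models without a baseline term, for aims that include change on treatment. The 80% carries over to a within-patient change only if the correlation is about 0.45 or higher. Adjusting an on-treatment level for baseline would gain about 2 to 14 points of raw-scale power over rho 0.3 to 0.7, and would lower the rate at which a baseline gap passes as a treatment-related difference: 5% against 15% to 54% if the gap regresses, 19% to 47% against about 84% if it persists.

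These figures assume normal data, a common SD, a 12 v 21 split, and both samples from all 33 patients. With fewer sampled patients the level comparison also weakens: 77% at N = 28 and 69% at N = 24, at about 35% responders.

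**What to change.** In 13.2 and 13.3:

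- Keep the two-sample t-test for the baseline level, labelled as the prognostic comparison.
- For the on-treatment level, fix one sample (first reimaging) and fit a linear model of the log level on response group, with the patient's own log baseline as covariate, one row per patient.
- In the logistic models, enter any on-treatment marker together with its baseline value.
- Name the change-score comparison as a sensitivity analysis, and say that a conclusion resting on only one of the two depends on whether the baseline gap regresses or persists.
- State that the 80% refers to a single level on the raw scale with coefficient of variation 0.45; give an assumed correlation, with a range, for any claim about change.
- Reconcile the sampling schedule in the synopsis and section 1.3 with sections 9.1.3, 9.2.3 and 9.3.3 and footnote 17 of 10.2.

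The cost is wording and one covariate (one degree of freedom) per model. No new patients are needed. No new samples are needed if the synopsis and 1.3 schedule governs; if the later draw stays tied to a change in response, there is no common fixed-time sample to analyse, and adjustment would not repair sampling times that differ by outcome. Patients lacking either sample drop out of the adjusted comparison, so their number should be reported.
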